7.5.2.2 Study 111-202

Analysis of safety data from the 6-month initial phase of Study 111-202 showed that treatment with BMN 111 for 6 months at doses of 2.5, 7.5, 15, and 30 µg/kg was generally well tolerated. In addition BMN 111 at 15 µg/kg was well tolerated for over 12 months with no new safety concerns identified.

Based on review of data from the Phase 2 clinical trial, injection site reactions and hypotension have been identified as risks associated with BMN 111 injections. Hypersensitivity reactions including development of BMN 111 antibodies are potential risks associated with BMN 111 injections. For a detailed summary of risks, please refer to the current version of the Investigator's Brochure supplied by BioMarin.

	Study 111-301 Amendment 4	Page 41
---	---------------------------	---------

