Concomitant medications ^y	X	X	X	X	X	X	X	X	X	X	X	X
BMN 111 or placebo administration ^z		X	X	X	X	X	X	X	X	X		
BMN 111 or placebo accountability		X	X	X	X	X	X	X	X	X		X
Adverse events ^{aa}	X	X	X	X	X	X	X	X	X	X	X	X
Capture procedures/ interventions/surgeries ^{bb}		X	X	X	X	X	X	X	X	X	X	X
Contact for Study Follow Up ^{cc}	Required every 4 weeks (± 10 days) after the Week 6 visit when there are no study visits or contact in the preceding 4 weeks ^{dd}											

NOTE: ALL BLOOD AND URINE LABORATORY ASSESSMENTS ARE PRE-DOSE EXCEPT WHEN SPECIFIED. OTHER ASSESSMENTS CAN BE CONDUCTED EITHER PRE-DOSE OR POST-DOSE UNLESS OTHERWISE SPECIFIED.

- ^a Day 10 visit has a ± 1-day window; all subsequent visits have a ±7-day window.
- ^b If both visits are on the same day, the 111-901 procedures that can be used as the 111-301 screening data are outlined in the Study Reference Manual.
- ^c Demographics, medical history, including ACH-related history, should include all major illnesses, diagnoses, and surgeries that the subject has ever had; including any prior or existing medical conditions that might interfere with study participation or safety.
- ^d Standing height of the subject's biological parents may be assessed (optional) via height measurement or stated height. Height measurement can be done at any point in the study. Prior to the measurement being taken, each parent is required to complete an ICF specific to parent height assessment. The ICF will be signed prior to the assessment, which can be done at any point in the study. If the biological parent is not available during the course of the study to take his/her standing height, if consented, the biological parent can provide his/her stated height.

	Study 111-301 Amendment 4	Page 48
---	---------------------------	---------

- e. If subjects had previous genetic testing, subjects must have either a written letter by the physician confirming genetic testing, including the specific mutation required for Study 111-301 include the identification of FGFR3 mutation (G346E, G375C, G380R, or “other”) OR a lab report from a certified laboratory with the study specific mutation documented.
- f. Complete physical exam includes all major body systems.

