All other visits	After at least 5 min of rest, subject's BP is taken 1 time in sitting position.	
Assessment Frequency post- dose		
Dosing Visits	0-1 hr post-dose	1-2 hr post-dose
Days 1	Q15 min (\pm 5 min)	Q 30 min (\pm 5 min)
Day 2 -3	Q30 min (\pm 5 min)	Q30 min (\pm 5 min)
All other dosing visits: vital sign measurements are taken once per time point in a sitting position after at least 5 minutes of rest.	Q30 min (\pm 5 min); for 1 hour	

Note: Please reference the Blood Pressure Instrument and Technique Guidelines document for additional information on blood pressure measurement requirements.

- i. Growth measures should be collected at approximately the same time each visit (\pm 2 hr from the time when the first measurement assessment was taken at Screening) by a study staff member, preferably the same person throughout the study, who has been trained by a BioMarin representative. Anthropometric measurements may include but are not limited to standing height; sitting height; weight; head circumference; upper and lower arm length; leg length; and arm span (See Anthropometric Measurement Guidelines). Anthropometric measurements will be taken three times in a row with the exception of weight, which is taken once. Anthropometric measurements will be taken at the early termination visit only if subject discontinues after Week 6 and $>$ 2 weeks since previous anthropometric measurement assessment.
- j. Reference the study-specific HRQoL and WeeFIM guidance documents. NOTE: for the Child Behavior Checklist (CBCL), no data will be collected from the language scale, as it is supplemental and not required to calculate any of the behavior measures.
- k. Hip clinical assessment: this assessment will include medical history of the hip and physical exam (including observation of gait when possible) to determine changes in hip function or pain with hip (active and passive range of motion, when possible). Changes from baseline may trigger further evaluation based on the investigator's clinical assessment.
- l. If sleep study results in a poor recording or is uninterpretable, the subject may need to repeat the assessment. Sleep study occurs at the early termination visit only if early termination visit occurs after Week 26 and subject has had a previous sleep study during the trial, ie, has entered the substudy.

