**Study 111-301 Statistical Analysis Plan****5 GENERAL ANALYSIS CONSIDERATIONS**

The analyses described in this SAP are based on Amendment 4 of the protocol (dated 01-February-2019).

Individual subject data that is reflected in data summaries will be provided in **PI**. Unless otherwise specified, all **PI** will be by treatment group and ordered by subject number, where subject number includes the site number.

Summary tables and figures are provided by treatment group with no overall population column. There are certain exceptions (e.g. subject disposition, demographics, baseline characteristics and safety data) which are indicated in the relevant sections.

Baseline annualized growth velocity (AGV) is defined in Section 14.3.1. Baseline growth measures (other than AGV) and baseline weight are those assessed on Day 1 of dosing, regardless of timing relative to dosing. (Note: If no assessments are available, then the baseline assessment will be the last non-missing assessment prior to Day 1). All other baseline assessments are the last non-missing on-study 301 assessments prior to administration of study drug. Change from baseline is calculated as: [post-baseline value – baseline value]; Percent change from baseline is calculated as: ([post-baseline value – baseline value]/baseline value) x 100.

The Screening visit will not be presented in descriptive summaries over time. When the analysis windows have been applied (see Section 5.4), data collected at the screening visit may be included in the Baseline assessment. All assessments will be listed, but only those assessments assigned to visits according to the windows applied (see Section 5.4) will be summarized in tables or graphically. Exceptions to this are summaries of the worst post-baseline laboratory data in shift tables where all assessments are considered, and also the standing height assessments displayed in the spaghetti plots.

Unless otherwise specified, the number of subjects, mean, 25th percentile, median, 75th percentile and estimates of precision (e.g. SD, confidence interval) will be displayed to one more decimal place than the collected data. Minimum and maximum values will be presented to the same decimal places as the collected data. For summaries by visit, the number of subjects with non-missing observations (n) according to the analysis windows (see Section 5.4 for further details) at the derived visit will be presented.

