14.5.2 Growth Measures

Each of the following anthropometric growth measures are recorded at Screening, Day 1, Week 13, Week 26, Week 39, and Week 52:

- Standing Height (cm)
- Sitting Height (cm)
- Upper Leg Length (Thigh) (cm)
- Knee to Heel Length (cm)
- Tibial Length (cm)
- Head Circumference (cm)
- Upper Arm Length (cm)
- Lower Arm (Forearm) Length (cm)
- Arm Span (cm)

In addition, a measure of lower body length will be calculated as follows:

- Lower Body Length (cm) = Standing height – Sitting height

Study 111-301 Statistical Analysis Plan

Baseline growth measures are those assessed on Day 1, regardless of timing relative to dosing. All summaries and analyses will be based on the FAS.

For each of the above growth measures (including lower body length), the absolute values at ≥ 12 Months Prior, ≥ 6 Months Prior, baseline, Week 26 and Week 52, and change from baseline at Week 26 and Week 52, will be summarized (n, mean, SD, median, 25th and 75th percentile, minimum, maximum) and presented by treatment group for each baseline age category (≥ 5 to < 8 , ≥ 8 to < 11 , ≥ 11 to < 15 , ≥ 15 to < 18 years).

Analysis:

Subjects with missing standing height at Week 52 will have standing height imputed, as described in Section 14.3.2. The same approach will be applied for missing sitting height assessments at Week 52.

With the exception of sitting height and standing height, no imputation will be applied for missing Week 52 assessments. Analyses will be based on observed data only.

For each growth measure, the null hypothesis of no difference between the BMN 111 group and the placebo group in the mean change from baseline at the Week 52 visit will be tested.

SAS PROC MIXED will be used to test the null hypothesis of no treatment difference using an ANCOVA model described below, for each of the above *growth measures*.

PROC MIXED;

CLASS Stratum Treatment;

MODEL Change from baseline in *growth measure* at Week 52 =
Baseline_*growth_measure* Baseline_AGV Baseline_Height_Z-score Treatment
Stratum;

LSMEANS Treatment /DIFF CL;

RUN;

For each growth measure, the least-squares (LS) mean change from baseline at Week 52 will be presented for each treatment group, along with the difference in LS means (calculated as BMN 111 – Placebo), the 95% confidence interval for the difference, and 2-sided p-value.

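### The Day 1 standing height, which enters both the baseline and the Week 52 growth velocity, may be measured after the first injection, when a reaction suggesting BMN 111 may already have been seen

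*Protocol*

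**What the plan says.** **Order of measurement and dose.** The note under Protocol Table 9.1.1 requires blood and urine samples before the dose unless stated otherwise, then says "OTHER ASSESSMENTS CAN BE CONDUCTED EITHER PRE-DOSE OR POST-DOSE UNLESS OTHERWISE SPECIFIED". Nothing in the table specifies otherwise for anthropometry. Footnote i says "Growth measures should be collected at approximately the same time each visit", meaning within 2 hours either side of the clock time used at Screening, when no dose is given. Protocol 9.12.2 repeats that window.

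**Who measures.** Footnote i has the measurement done "by a study staff member, preferably the same person throughout the study, who has been trained by a BioMarin representative". Neither document separates this person from dosing, post-dose blood pressure checks or adverse event questioning. SAP 4.6.1 describes the masking plan in terms of PK and biomarker data only.

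**Baseline definition.** SAP Section 5 states: "Baseline growth measures (other than AGV) and baseline weight are those assessed on Day 1 of dosing, regardless of timing relative to dosing". SAP 14.5.2, whose list of growth measures includes standing height, says the same: "Baseline growth measures are those assessed on Day 1, regardless of timing relative to dosing". All other baselines in SAP Section 5, apart from AGV, must come before study drug. AGV is referred to SAP 14.3.1, which uses the date of Day 1 and sets no order relative to the dose.

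**What can be seen after the first dose.** Protocol 7.5.2.2 says that "injection site reactions and hypotension have been identified as risks associated with BMN 111 injections". On Day 1 the child is observed for at least 2 hours, with blood pressure every 15 minutes in the first hour and every 30 minutes in the second. Injection-site photographs are optional but encouraged on that day.

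**The concern.** Protocol 9.2 justifies the double-blind placebo design partly as protection against bias in data collection. Standing height is read by a person, and it feeds the primary endpoint and both key secondary endpoints.

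A site that follows the plan exactly may randomize the child, inject, watch for up to 2 hours, and only then measure the height that serves as baseline. If the measurer has meanwhile noticed redness at the injection site or a fall in blood pressure, that reading is no longer taken in ignorance of a clue to allocation. A Day 1 reading taken before the first dose cannot be influenced by any reaction to the drug.

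Day 1 is the worst visit at which to leave this open, because its height is used twice in the primary endpoint, with opposite signs.

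**Working it through.** **The plan's own figure.** Protocol 14.6 and SAP 4.5 assume 55 per arm, a difference of 1.75 cm/yr, SD 2.80 and two-sided alpha 0.05. The standard error is 2.80 × √(2/55) = 0.534. Power is Φ(1.75/0.534 − 1.96) = 90.6% by the normal approximation and 90.1% by the exact noncentral t, so the stated figure of about 90% reproduces. Nothing below changes it.

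**Inputs for the leverage.**
- AGV formula and intervals: Protocol 14.2.1 and SAP 14.3.1.
- On-treatment interval: 364 days (target Day 365, SAP Table 5.4.2).
- Baseline interval: 182 to 363 days (window for the visit at least 6 months prior, SAP Table 5.4.1).

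**Raw change from baseline.** Let H0 be the earlier 111-901 height, H1 the Day 1 height, H52 the Week 52 height, and d the baseline interval in days.

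Change = (H52 − H1) × 365.25/364 − (H1 − H0) × 365.25/d

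The weight on H1 is −(365.25/364 + 365.25/d):
- d = 182: −(1.003 + 2.007) = −3.01
- d = 363: −(1.003 + 1.006) = −2.01

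The weight on H52 is only +1.003.

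**After ANCOVA.** Let b be the within-arm slope of Week 52 AGV on baseline AGV. If Day 1 is under-read by e in one arm, the adjusted difference shifts by e × (1.003 + b × 365.25/d). With d = 182 this is 1.00e at b = 0, 2.01e at b = 0.5 and 3.01e at b = 1. The slope is not given, so 0 to 1 is an assumed range. The model also contains baseline height Z-score, which comes from the same reading; that extra term is left out here.

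**From one reading to the arms.** Only a difference between arms biases the comparison. Let q be the net share of children affected, that is, the proportion of the BMN 111 arm measured post-dose and read differently because of a visible reaction, minus the same proportion on placebo. Then bias = q × e × leverage. The documents give neither q nor e. For an assumed e = 0.1 cm, d = 182 and leverage from 1 to 3:

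| Assumed q | Bias (cm/yr) | Share of 1.75 | Chance of a false positive favouring BMN 111 (nominal 2.5%) |
|---|---|---|---|
| 0.25 | 0.025 to 0.075 | 1% to 4% | 2.8% to 3.4% |
| 0.5 | 0.05 to 0.15 | 3% to 9% | 3.1% to 4.6% |
| 1 | 0.10 to 0.30 | 6% to 17% | 3.8% to 8.0% |

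The last column uses the planning SD without covariate adjustment and assumes Day 1 is under-read. Bias scales in proportion to e.

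**Sign.** Over-reading at Day 1 reverses every entry. If suspected-drug children were read high by s at both Day 1 and Week 52, the raw change would move by 1.003s − 3.010s = −2.007s, against BMN 111. After ANCOVA this is −2.007 × b × s, which is 0 at b = 0.

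**The case against.** **The reactions do not reveal the treatment.** A reader might infer that a visible reaction identifies BMN 111. The documents do not support that. Hypotension in the Phase 1 study (Protocol 7.2.1) was more frequent than on placebo, but mild and mostly asymptomatic. The Phase 2 study was open-label, so its injection-site data have no placebo rate beside them. Placebo contains the same excipients and is also injected daily (Protocol 9.4.2.1). This objection stands: the reactions are suggestive at most. One qualification is that an asymptomatic fall in blood pressure is still seen by whoever records it.

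**The size is assumed and the sign is open.** This also stands. The schedule permits post-dose measurement and does not require it. Placebo reactions offset reactions on drug. Triplicate readings, trained measurers and standardised equipment limit how far a reading can drift. A reader might infer a bias in favour of BMN 111, but the sign calculation shows that it could run either way.

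**Later visits.** A reader might also infer that every height must be taken before the dose to protect the blind. That would achieve little. By Week 13 staff have attended several dosing visits and asked about adverse events, so a pre-dose reading does not remove what they know. It may also conflict with the clock window of ±2 hours and the child's usual injection time. None of this applies on Day 1, when there is no earlier reaction to recall and no usual dosing time yet.

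**Unseen documents.** The Anthropometric Measurement Guidelines and the masking plan are not available here and may set an order. They would still have to be reconciled with the SAP's express acceptance of either order.

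**Conclusion.** The concern holds for Day 1. The plan allows the height on which both AGV intervals turn to be read after the first dose and after up to 2 hours of observation, and the SAP accepts that value although it requires most other baselines to precede study drug.

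What the documents establish is leverage, not bias: about 3.0 cm/yr per cm of Day 1 error in the raw change with a 182-day baseline interval, about 2.0 with 363 days, and about 1.0 to 3.0 after ANCOVA with 182 days and a slope between 0 and 1. Any actual effect depends on the between-arm difference in visible reactions, on how often sites measure post-dose, and on how far a reading would shift. None of these is given.

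This is an avoidable weakness in the blind on the primary endpoint that is cheap to close. It is not evidence that the result would be wrong.

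**What to change.** - **Protocol, Table 9.1.1 footnote i and 9.12.2:** require Day 1 anthropometry to be completed before the first injection.
- **SAP 5, 14.3.1 and 14.5.2:** define baseline growth measures, and the Day 1 height used in AGV, as the pre-dose Day 1 value. Keep the existing fallback to the last value before Day 1.
- **Day 1 heights already taken post-dose:** retain them in the primary analysis as a stated exception. Add a sensitivity analysis that replaces them with the last pre-dose (Screening) height at its actual date. If the order of measurement and dose was not recorded, use the Screening height for all subjects in that analysis.
- **Weeks 13 to 52:** pre-dose measurement is optional, for the reasons given above.

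**Cost.** No staff or procedure is added, because anthropometry is already done at Screening and on Day 1; the first injection waits for the measurement. The sensitivity analysis has a price in precision. With Screening on Day −30, a 182-day baseline interval shrinks to 182 − 30 = 152 days, and the later interval grows to 364 + 30 = 394 days, of which 30 are untreated. It should therefore support the primary analysis and not replace it.

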- ^x Injection site photos are optional, but sites are strongly encouraged to take photos on Day 1, Week 26, Week 52, and Early Term Visit. During a scheduled visit, photos of the injection site will be taken in either of these two situations: 1) If an injection site reaction (ISR) occurs, photos will be taken for each ISR when it becomes apparent (or at onset), at most severe, and then post resolution. The time of the post-resolution photo may not be the same as the time the AE resolved, and this is expected. If the visit has ended and the ISR has not resolved, the subject is not expected to remain on site until ISR resolves. If the ISR is ongoing at the end of the visit, record as an ongoing AE. 2) If the subject has not had an ISR by the end of the study visit, a photo will still be taken of the injection site used on that day. In between visits, if an ISR worsens or changes in pattern, then the subject should have an unscheduled site visit. During the visit photos of the injection site with the ISR should be taken. Also, injection sites may be photographed if there is a new ISR or at any other time at the discretion/medical judgment of the investigator or as recommended by the sponsor.
- ^y All medications (prescription, over-the-counter and herbal) and nutritional supplements taken 30 days prior to Screening and throughout the study should be documented.
- ^z The same injection site should not be used 2 days in a row, and should be rotated between the four injection sites bilaterally (upper thigh, upper back of arm, abdomen or buttocks).

	Study 111-301 Amendment 4	Page 51
---	---------------------------	---------

- ^{aa.} After written informed consent but before study treatment initiation, only SAEs associated with protocol-imposed interventions will be recorded. After study drug initiation, all AEs and SAEs will be recorded until 4 weeks after either the last administration of study drug or the Early Termination visit. In the event of pregnancy the reporting period will be 12 weeks after either the last administration of study drug or the Early Termination visit. If a subject is discontinued from the study prematurely, AEs and SAEs will be recorded at the Early Termination visit.

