- ^{bb.} All procedures/interventions/surgeries will be recorded after informed consent is obtained and after the first administration of study drug, until 4 weeks after either the last administration of study drug or the Early Termination visit. If a subject is discontinued from the study prematurely, all procedures/interventions/surgeries will be recorded at the Early Termination visit.
- ^{cc.} Contact by a study staff member to the caregiver will be required after the Week 6 visit every 4 weeks (± 10 days) when there are no study visits or contact in the preceding 4 weeks. During these contacts, study staff will ask about dose administration and seek information on AEs and SAEs by specific questioning. Information on all AEs and SAEs should be recorded in the subject's medical record and on the AE eCRF.
- ^{dd.} The 4-week safety follow up visit will be waived for subjects who enter BMN 111 study 111-302 within the 2-week period following last dose of study drug. If sponsor discontinues development program at any time, a 4-week safety follow-up visit should occur.

	Study 111-301 Amendment 4	Page 52
---	---------------------------	---------

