9.3.4 Removal of Subjects from Treatment or Assessment

Subjects (or their legally authorized representative) may withdraw their consent to participate in the study at any time without prejudice. The investigator must withdraw from the study any subject who requests to be withdrawn. A subject's participation in the study may be discontinued at any time at the discretion of the investigator and in accordance with his/her clinical judgment. When possible, the tests and evaluations listed for the termination visit should be carried out. BioMarin must be notified of all subject withdrawals as soon as possible.

Investigators may discontinue administration of BMN 111 or placebo at any time. Reasons for which the investigator or BioMarin will withdraw a subject from study treatment include, but are not limited to, the following:

1. Evidence of both (1) growth plate fusion as assessed by radiographic imaging of distal femur and proximal tibial and (2) decreased AGV ($AGV < 1.5 \text{ cm/yr}$) as assessed over a period of at least 6 months. In case of discordant imaging and AGV, subject continuation will be discussed with BioMarin Medical Monitor, Principal Investigator and the DMC.
2. Subject experiences a serious or intolerable AE due to BMN 111 as determined by the investigator or sponsor.
3. Subject requires medication or medical procedure prohibited by the protocol.
4. Subject does not adhere to study requirements specified in the protocol.
5. Subject is lost to follow-up.
6. Subject becomes pregnant (refer to Section 10.3.1.11 for details on the reporting procedures to follow in the event of pregnancy).

If a subject fails to return for scheduled visits, documented effort must be made to determine the reason. If the subject's caregiver cannot be reached by telephone, a certified letter should be sent to the subject (or the subject's legally authorized representative, if appropriate) requesting that he or she contact the investigator. A copy of this letter and any response should be kept in the subject study records. If the subject cannot be contacted or does not respond, the subject will be considered lost to follow-up.

The investigator (or designee) must explain to each subject before enrollment into the study that the subject's protected health information obtained during the study may be shared with

	Study 111-301 Amendment 4	Page 58
---	---------------------------	---------

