BioMarin, regulatory agencies, and the IRB/IEC/REB. It is the investigator's (or designee's) responsibility to obtain written permission to use protected health information per country-specific regulations, such as the Health Insurance Portability and Accountability Act of 1996 (HIPAA) in the USA, from each subject (or the subject's legally authorized representative). If permission to use protected health information is withdrawn by the subject, it is the responsibility of the investigator to obtain a written request from the subject to ensure that no further data will be collected from the subject. The subject will then be removed from the study.

It is a priority of the study to maximize study subject retention and adherence to study-specific procedures. The completeness of the study data may affect the integrity and accuracy of the study results. Therefore, subjects who discontinue study treatment should be encouraged to continue to undergo as many of the protocol-specified procedures and assessments as possible for the remainder of the study, as long as such continued participation does not detrimentally affect the health, safety, or welfare of the subject and consent remains in place. It is important that following treatment discontinuation the original visit schedule is strictly adhered to.

For subjects who discontinue BMN 111 or placebo but remain in the study, PK and BMN 111 activity assessments will be waived completely; vital signs and clinical labs/biomarkers will be obtained only once at each visit subsequent to BMN 111 or placebo discontinuation. Pre-and post-dose designations will not apply as the subject has discontinued dosing and vital sign and clinical lab/biomarkers assessments previously designated as "post-dose" will be waived. All other assessments at each visit should be completed if possible and the subject is willing. Data from the study procedures and assessments may be used to further characterize the natural progression of ACH.

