10.2 Methods and Timing for Capturing and Assessing Safety Parameters

10.2.1 Adverse Event Reporting Period

The study AE reporting period is as follows: after informed consent but prior to initiation of study treatment, only SAEs associated with any protocol-imposed interventions will be reported. After informed consent is obtained and the first administration of study drug, all non-serious AEs and SAEs reporting period begins and continues until 4 weeks following either the last administration of study drug or the Early Termination visit, whichever is longer (refer to Section 12.4). The criteria for determining, and the reporting of, SAEs is provided in Section 10.1.2.

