This approach addresses the same estimand as the primary analysis except that the intercurrent event, defined as rescue treatment for achondroplasia, is handled differently. In the event that a subject has been receiving rescue medication from the start of the study, they

Study 111-301 Statistical Analysis Plan

will be excluded from this supplementary analysis. The analysis will be conducted on imputed data, as described for the primary analysis; however, any assessments that are measured following either limb lengthening or growth hormone/ gonadotropin-releasing hormone will be excluded from this analysis. The ANCOVA model described in the primary analysis will be applied, and the estimator will be the difference between the two randomized groups in the mean change from baseline in AGV at Week 52.

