15.7 On-Study Procedures, Interventions and Surgeries

Any procedures, interventions or surgeries that occur on study (post first dose of study drug) will be captured, along with start and stop date. These will be coded using the latest available MedDRA version and details provided in a listing.

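### For a child who stops study drug but stays to Week 52, the written recording window for procedures, AEs and SAEs closes 4 weeks after the last dose, and it conflicts with passages that call for continued capture

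*Protocol*

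**What the plan says.** The window is written in five places in the protocol.

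- Table 9.1.1, footnote bb: procedures, interventions and surgeries are recorded "after the first administration of study drug, until 4 weeks after either the last administration of study drug or the Early Termination visit". Section 9.12.6.2 repeats this.
- Table 9.1.1, footnote aa: "all AEs and SAEs will be recorded until 4 weeks after either the last administration of study drug or the Early Termination visit".
- Section 10.2.1: the AE and SAE reporting period "continues until 4 weeks following either the last administration of study drug or the Early Termination visit, whichever is longer". Section 10.4.1 gives the same end for SAEs.

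Other passages assume that capture goes on while the child stays in the study.

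- Table 9.1.1 and Section 12.2 list both adverse events and procedures at Weeks 13, 26, 39 and 52, with no exception for children off drug.
- Section 9.3.4 keeps these children on the original visit schedule. It waives PK, activity markers and post-dose checks, then adds: "All other assessments at each visit should be completed if possible and the subject is willing".
- Section 10.2.2 has investigators ask about AEs at every contact.
- SAP 15.7: "Any procedures, interventions or surgeries that occur on study (post first dose of study drug) will be captured". It states no 4-week limit.

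SAP 14.1 includes heights measured after treatment discontinuation. Supplementary Analysis 2 (SAP 14.3.3) then states that "any assessments that are measured following either limb lengthening or growth hormone/ gonadotropin-releasing hormone will be excluded from this analysis".

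**The concern.** The plan deliberately retains children who stop drug, and it uses their heights. The recording rule is tied to dosing instead of to study participation, so for these children it can expire long before the last height is taken.

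Two uses of the data are exposed. First, Supplementary Analysis 2 can drop heights after limb lengthening only if the operation and its date are in the database. Among the reasons for withdrawing study treatment, Protocol 9.3.4 lists "Subject requires medication or medical procedure prohibited by the protocol". An operation regarded as prohibited could therefore come after the last dose. Second, SAE reporting (10.4.1) and the recording of deaths (10.3.1.10) are tied to the reporting period in 10.2.1. Fracture, slipped capital femoral epiphysis and avascular necrosis are the protocol's events of special interest (10.1.3), and that section gives them no recording period of their own.

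**Working it through.** **The plan's own figure.** This point disputes no number. For completeness, the planned power reproduces: with 55 per arm, a difference of 1.75 and an SD of 2.80 (Protocol 14.6), the noncentrality is 1.75 / (2.80 × √(2/55)) = 3.28. On 108 degrees of freedom at two-sided 0.05 this gives 90.1%, against the stated 90% or so.

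**Which anchor applies.** The window has two anchors, the last dose and the Early Termination visit. Footnote aa links the Early Termination visit to leaving the study early. A child who stops drug and attends to Week 52 does not leave early, so only the last dose remains. The later-of qualifier in 10.2.1 and 10.4.1 then has nothing to choose between; footnote bb and 9.12.6.2, which govern surgery, do not contain it. If a site did hold an Early Termination visit when drug was stopped, the end date would be much the same.

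**Length of the gap.** For a last dose in week s, the window closes at week s + 4. The time left to Week 52 is max(0, 52 − (s + 4)). Height visits are at Weeks 13, 26, 39 and 52 (Table 9.1.1).

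| Last dose (week) | Window closes (week) | Weeks to Week 52 outside it | Height visits after it closes |
|---|---|---|---|
| 6 | 10 | 42 | 13, 26, 39, 52 |
| 13 | 17 | 35 | 26, 39, 52 |
| 26 | 30 | 22 | 39, 52 |
| 39 | 43 | 9 | 52 |
| 48 | 52 | 0 | none |

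Every last dose before Week 48 leaves the Week 52 height, on which the endpoint rests, after the window has closed.

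**Procedures against AEs.** The contacts required every 4 weeks (9.1, 12.5) ask about dosing, AEs and SAEs, and answers go on the AE eCRF. They do not ask about surgery. Procedures therefore depend on the visit checklist, which conflicts with footnote bb. Medications are documented throughout the study (footnote y, 9.4.8), so growth hormone and GnRH use has no such cut-off.

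**Rules that might fill the gap.** Section 10.6 covers deaths and SAEs after a child's participation has ended, and only if the investigator thinks them possibly related. A retained child is still participating, so neither 10.4.1 nor 10.6 applies as written once the 4 weeks have passed. Section 10.7 does run to the last study visit, but only for events that may need urgent safety measures.

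**The case against.** The strongest reply is that the documents already call for continued recording: the checklist at each visit, the short list of waived items in 9.3.4, questioning at every contact, and SAP 15.7. A site following the schedule would miss little. That stands against reading the plan as forbidding or ending all capture after 4 weeks. It does not settle the matter, because the window is the only text with an explicit end date and no passage ranks the two rules.

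A reader might infer more than the documents support, in four ways.

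- *That every child off drug loses coverage.* One who later leaves through an Early Termination visit is covered to 4 weeks after that visit.
- *That the primary result is biased.* Suppose a surgical gain of 3 to 10 cm, a figure not in the documents. One case in 55 moves an arm mean by 3/55 = 0.05 to 10/55 = 0.18 cm/year, which is 3% to 10% of 1.75. But the primary estimand takes in heights after rescue or discontinuation by design (SAP 14.1, 14.3.2), so this shift occurs whether or not the surgery is recorded. Only Supplementary Analysis 2, which is non-confirmatory, could change. Protocol 7 describes limb lengthening as taking 2 to 3 years, so the gain by Week 52 is uncertain.
- *That the Per-Protocol set is contaminated.* Criterion 4 in SAP 5.1.2 requires completed treatment, so early stoppers already fail it.
- *That such surgery is likely.* Planned or expected limb lengthening is exclusion 14, and the documents give no rate or timing.

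On safety, 10.1.3 runs its 24-hour rule from site awareness and could be read as having no end date. Hip assessments and centrally read leg X-rays continue. These make it likely that a site would learn of an event; they do not place it inside the period in 10.2.1. It is also true that SAP 15 stops its safety tables 30 days after discontinuation, so later events would appear only in listings.

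**Conclusion.** The point holds as an unresolved contradiction about children retained off drug, sharper for procedures than for AEs. If the stated window is followed, Supplementary Analysis 2 may lack the surgery date it depends on. SAEs, deaths and skeletal events in a child still being seen would also fall outside the mandatory reporting period, for 35 weeks to Week 52 after a Week 13 stop and 22 weeks after a Week 26 stop.

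This assumes that the child has no later Early Termination visit and that the site applies the window literally. The number of children affected cannot be derived from the documents and should be small. The primary analysis and the power do not change, and the Per-Protocol set is largely untouched. The wording should still be corrected, because the safety side concerns children and the repair is cheap.

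**What to change.** Reconcile footnotes aa and bb and Sections 9.12.6.2, 10.2.1 and 10.4.1. State in each that procedures and surgeries, AEs, SAEs and events of special interest are recorded until the later of 4 weeks after the last dose and the child's last study visit, including children who remain in the study off drug. This matches SAP 15.7 and resembles the last-visit anchor already used in Protocol 10.7. Adding a question about procedures to the 4-weekly contacts would close the remaining weak spot.

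The SAP can keep its 30-day safety tables, with a sentence saying that later events are listed separately.

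The cost is wording in five places and a few more eCRF entries. No new visits are needed, because these children already attend on schedule and their caregivers are already contacted.
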